where id is a participant study identifier, trtrnd is the randomly assigned treatment group, visit is the visit identifier, Value is value of the efficacy endpoint being tested for a given participant at a given visit, sx2b1 is years since ALS symptom onset centered at the sample median, dFRS is pre-baseline slope centered at the sample median, r1z is an indicator of riluzole use at baseline, and edv is an indicator of edaravone use at baseline. The primary estimate will be the treatment-dependent difference in change from baseline to the Week 24 Visit. The estimate and its 95% Wald confidence bounds will be obtained by a linear contrast of adjusted means. The following SAS code specifies the linear contrast for a regimen with one active treatment assuming an endpoint measured every 8 weeks and that the sort order for treatment group has the active group last and visits are sorted chronologically:

```
estimate "3|Act vs Plb|dWk 24" trtrnd*visit 1 0 0 -1 -1 0 0 1 / cl;
```

A significant difference in 24-week change from baseline in the direction of greater improvement or less worsening among participants randomized to active treatment would support inference of benefit from active treatment for the efficacy endpoint being tested.

The estimand estimated by the primary linear contrast of the repeated-measures linear mixed model is the mean difference in 24-week change from baseline of a given continuous efficacy endpoint in the active treatment group relative to the placebo group in the FAS population. The estimand is defined by the following attributes:

- Treatment: verdiperstat administered orally at a dosage of 600 mg BID vs. placebo.
- Population: FAS population as defined in Section 6.1.
- Variables: absolute change in endpoint from baseline to the Week 24 Visit.
- Intercurrent event: treatment discontinuation: handled via treatment policy approach, all data will be used including data collected during the placebo-controlled period after treatment discontinuation. Missing data post-treatment, including data missing due to death, will not be imputed, handled via missing at random assumption.
- Population-level summary: difference in conditional means of active treatment relative to placebo.

Inference from this analysis is supportive of inference from the Bayesian shared-parameter, repeated-measures model for the primary endpoint and is the primary analysis for secondary

endpoints. A separate supportive analysis will include centered baseline serum NfL level and the interaction of centered baseline serum NfL level and visit as additional covariates.

# 6.5.3 Random-slopes Model

The specification of the random-slopes linear mixed model and the primary linear contrast for estimating differences in mean rate of progression in a given continuous efficacy endpoint (ALSFRS-R total and domain scores, HHD upper extremity, lower extremity, and global average percentages, SVC, FVC by home spirometry, quantitative voice characteristics, serum creatinine, serum NfL, ALSAQ-40 domain scores and SI, and CNS-BFS total score) are revised from those specified in the M-SAP to include a main effect of treatment and to specify that study months are calculated as the difference in days from the Baseline Visit to the date of assessment of a given endpoint multiplied by 12 / 365.25.

The model will include fixed terms for month since the Baseline Visit, treatment group, treatment group × month interaction, centered years since ALS symptom onset and centered years since ALS symptom onset × month interaction, centered delta-FRS and centered delta-FRS × month interaction, centered baseline riluzole use and centered baseline riluzole use × month interaction, and centered baseline edaravone use and centered baseline edaravone use × month interaction. The following equations describe the model with regimen random effects:

$$Y_{ij} = \gamma_1 + a_{k(i)}^0 + b_i^0 + \gamma_2 t_i + \gamma_3' \mathbf{z}_i$$

$$+ \left(\gamma_4 + a_{k(i)}^1 + b_i^1 + \gamma_5 t_i + \gamma_6' \mathbf{z}_i\right) m_{ij} + \epsilon_{ij}$$

$$\{a_k^0, a_k^1\} \sim N(\mathbf{0}, \mathbf{\Sigma}_r), \{b_k^0, b_k^1\} \sim N(\mathbf{0}, \mathbf{\Sigma}_p), \epsilon_{ij} \sim N(\mathbf{0}, \sigma_\epsilon^2)$$

$$Cov(\mathbf{a}_k, \mathbf{b}_k) = \mathbf{0}, Cov(\mathbf{a}_k, \boldsymbol{\epsilon}_{i\cdot}) = \mathbf{0}, and Cov(\mathbf{b}_k, \boldsymbol{\epsilon}_{i\cdot}) = \mathbf{0}$$
(eqn. 2)

where  $Y_{ij}$  is a given efficacy endpoint measured in participant i at visit j,  $a^0_{k(i)}$  and  $a^1_{k(i)}$  are random intercept and slope for regimen k to which participant i was assigned,  $b^0_i$  and  $b^1_i$  are random intercept and slope for participant i,  $z_i$  is the vector of covariates (centered time since onset, centered delta-FRS, centered baseline riluzole use, and centered baseline edaravone use) for participant i,  $m_{ij}$  is the time from baseline to observation j for participant i in months calculated as days x 12 / 365.25,  $t_i$  is an indicator variable for treatment t to which participant i was assigned,  $\gamma_1$ ,  $\gamma_2$ ,  $\gamma_3$ ,  $\gamma_4$ ,  $\gamma_5$ , and  $\gamma_6$  are estimated parameters and vectors of parameters for the fixed effects, and  $\epsilon_{ij}$  is the residual for observation j for participant i. The regimen-specific random effects are normally distributed with mean  $\mathbf{0}$  and unstructured covariance matrix  $\mathbf{\Sigma}_r$ . The participant-specific random effects are normally distributed with mean  $\mathbf{0}$  and unstructured covariance matrix  $\mathbf{\Sigma}_p$ . The residuals for a given participant are normally distributed with mean  $\mathbf{0}$  and variance  $\sigma^2_{\epsilon}$ . The regimen-specific random effects, participant-specific random effects, and residuals are uncorrelated.

The following SAS code specifies the model:

where month is time in months from the Baseline Visit (assuming 12 months in an average of 365.25 days per year) and other fields are the same as identified above in Section 6.5.2. The primary estimand will be the treatment-dependent difference in slopes. The estimate and its 95% Wald confidence bounds will be obtained by a linear contrast of adjusted means. The following SAS code specifies the linear contrast for a regimen with one active treatment assuming that the sort order for treatment group has the active group last:

```
estimate "3|Act vs Plb|Slope (/mn)" month 0 trtrnd*month -1 1 / cl;
```

A significant difference in slopes in the direction of greater improvement or less worsening among participants randomized to active treatment would support inference of benefit from active treatment for the efficacy endpoint being tested.

The estimand estimated by the primary linear contrast of the random-slopes linear mixed model is the difference in mean rate of progression of a given continuous efficacy endpoint in the active treatment group relative to the placebo group in the FAS population. The estimand is defined by the following attributes:

Treatment: verdiperstat administered orally at a dosage of 600 mg BID vs. placebo.

Population: FAS population as defined in Section 6.1.

Variables: mean rate of change in endpoint from baseline to the Week 24 Visit.

Intercurrent event: treatment discontinuation: handled via treatment policy approach, all data will be used including data collected during the placebo-controlled period after treatment discontinuation. Missing data post-treatment will not be imputed, handled via missing at random assumption.

Population-level summary: difference in conditional mean slopes of active treatment relative to placebo.

Inference from these analyses is supportive of inference from the Bayesian shared-parameter, repeated-measures model for the primary endpoint and inference from the repeated-measures linear mixed model for secondary endpoints. A separate supportive analysis will include centered baseline serum NfL level and the interaction of centered baseline serum NfL level and study month as additional covariates.

#### 6.5.4 Survival and Time to Clinical Events

Survival and time to hospitalizations and clinical events will be analyzed in the FAS, ECM, ERO, EPP, STF, SFN, and SRO analysis sets. Survival analyses that include follow-up beyond the placebo-controlled period will be analyzed in the ERO analysis set. The summaries and analyses of time to death or death equivalent are the same as specified in the M-SAP with the revision to include baseline age as an additional covariate in adjusted models, with the addition that the endpoints of time to death independent of occurrence of death equivalents and time to each of the hospitalization and clinical events will be separately analyzed using the same models, and with an additional adjusted analysis that includes baseline serum NfL level as a covariate. Analysis of time to King's stage 4a or 4b will accommodate interval censoring between ALSFRS-R assessments and will be stratified by baseline King's stage.

#### 6.5.5 CAFS

The primary CAFS analysis is as specified in the MPRDR. Additional, unadjusted CAFS analyses are the same as specified in the M-SAP, including specification that pair-wise comparison of change in ALSFRS-R total score for participants who cannot be ranked by time to death or death equivalent is to the maximum follow-up time at which both participants have an observation, and with the following additions:

- 1. HHD upper and lower extremity percentage and SVC will be analyzed by CAFS by substituting change from baseline for those secondary efficacy endpoints in place of ALSFRS-R total score,
- 2. An additional set of CAFS analyses will use multiple imputation to extend follow-up of ALSFRS-R total score, HHD upper and lower extremity percentage and SVC for participants who early terminate, withdraw consent, or are lost to follow-up,
- An additional set of CAFS analyses for ALSFRS-R total score, HHD upper and lower extremity percentage and SVC will use time to death alone independent of any death equivalent,
- 4. An additional set of CAFS analyses for ALSFRS-R total score, HHD upper and lower extremity percentage, and SVC will adjust rank scores in a linear model with the following covariates: time from ALS symptom onset, delta-FRS, baseline use of riluzole, and baseline use of edaravone, and
- 5. An additional set of CAFS analyses for ALSFRS-R total score, HHD upper and lower extremity percentage, and SVC will adjust rank scores in a linear model with the following covariates: time from ALS symptom onset, delta-FRS, baseline use of riluzole, baseline use of edaravone, and baseline serum NfL level.

The multiple imputation model used to extend follow-up of functional scores for participants who early terminate, withdraw consent, or are lost to follow-up will use linear regression with covariates of time since symptom onset, delta-FRS, baseline riluzole use, baseline edaravone use, and each observed functional score prior to a missing assessment.

Inference from CAFS analyses is supportive of inference from the Bayesian shared-parameter, repeated-measures model for the primary outcome and supportive of inference from the repeated-measures model for the secondary outcomes of HHD upper extremity score, SVC, and HHD lower extremity score. Primary inference from CAFS analyses will compare survival by time to death or death equivalent, will compare change in function to the last jointly observed time point, and will adjust for the specified covariates.

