# 6.5.8 Placebo Multiple Imputation

Placebo multiple imputation analyses are the same as specified in the M-SAP and will be applied to ALSFRS-R total score, HHD upper and lower extremity percentages, and SVC.

The following SAS code specifies the imputation for an endpoint measured every 8 weeks:

where Wk00, Wk08, Wk16, and Wk24 are the values of a given efficacy endpoint at the Baseline, Week 8, Week 16, and Week 24 Visits, respectively, trtnd has a value of zero (0) for participants randomized to placebo, and x and y take appropriate values to specify the range of a given outcome measure (i.e., 0 and 48 for ALSFRS-R total score; 0 and . for HHD upper and lower extremity percentages and SVC).

Inference from these analyses is supportive of inference from the Bayesian shared-parameter, repeated-measures model for the primary endpoint and assess sensitivity to the missing data assumption of the repeated-measures linear mixed model for secondary endpoints in the FAS analysis set. A separate analysis will include centered baseline serum NfL level as an additional covariate in both imputation stages.

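### The imputation model for the extended-follow-up CAFS analyses leaves out randomised treatment, so when the drug works those analyses recover only part of the effect that full follow-up would show

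*SAP*

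**What the plan says.** SAP Section 6.5.5 lists five additions to the CAFS analyses carried over from the Master SAP. The second "will use multiple imputation to extend follow-up of ALSFRS-R total score, HHD upper and lower extremity percentage and SVC" and applies "for participants who early terminate, withdraw consent, or are lost to follow-up". The section's closing paragraph on imputation gives the model in full: it "will use linear regression with covariates of time since symptom onset, delta-FRS, baseline riluzole use, baseline edaravone use". The only other predictors are the participant's own earlier results, described as "each observed functional score prior to a missing assessment". Randomised treatment is not named. The text does not say that imputation is done by arm, and does not describe the model as placebo-based or conservative.

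The same section fixes the standing of these analyses. "Inference from CAFS analyses is supportive of inference from the Bayesian shared-parameter, repeated-measures model for the primary outcome", and likewise for the HHD and SVC secondary outcomes. The version used for primary CAFS inference "will compare change in function to the last jointly observed time point", so it is not the imputed one.

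Two other sections matter for comparison. Section 6.5.2 puts treatment and its interaction with visit into the mixed model for the same endpoints. Section 6.5.8 is a separate placebo-based imputation of the same four endpoints ("Placebo multiple imputation analyses are the same as specified in the M-SAP"), and it defines a treatment variable that "has a value of zero (0) for participants randomized to placebo".

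**The concern.** The imputed scores are used to compare arms. A regression fitted to both arms together, without a treatment term, gives an active and a placebo participant with the same covariates and the same scores so far the same expected next score. Any further separation after dropout is lost, except for what the earlier scores already carry. A participant who leaves soon after baseline has almost nothing in those scores to carry it.

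The stated aim of this set is to extend follow-up. A comparison restricted to shared visits loses effect because pairs are compared early, when less separation has built up. Extending follow-up should restore that loss, and a pooled model restores only some of it. A reader could then take the remaining shortfall for a real feature of the participants who left. The set covers the primary endpoint and three of the four key secondary endpoints.

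**Working it through.** The plan states no figure for the imputed CAFS analyses, so there is nothing to reproduce. The check is by simulation.

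**Inputs from the documents.** 120 active and 40 placebo in the regimen (protocol, RSA Summary); shared placebo from regimens A and C (SAP 6.1); 24 weeks of follow-up; 30% slowing and 5% mortality as illustrative values (protocol, Table 10.2.3); imputation covariates as in SAP 6.5.5.

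**Assumed inputs.** 120 placebo in total (3 × 40); placebo slope −1.1 points/month, slope SD 0.75, residual SD 1.5, baseline SD 5.5; dropout unrelated to outcome. The regimen tables name dropout scenarios but give no rates, so a range is shown.

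**Method.** ALSFRS-R every four weeks; sequential linear-regression multiple imputation on the listed covariates and prior scores, without and then with treatment; 5 imputations; 400 trials per setting. The CAFS effect is measured as

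win difference = P(active ranks better) − P(placebo ranks better), with deaths ranked first,

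and each result is divided by the complete-data value. In the early pattern the last visit is baseline, Week 4 or Week 8. In the spread pattern it falls anywhere from baseline to Week 20. Ratios were taken before rounding.

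| Dropout | Complete data | As written | Ratio | With treatment | Ratio |
|---|---|---|---|---|---|
| 10% spread | 0.223 | 0.210 | 0.94 | 0.223 | 0.997 |
| 10% early | 0.222 | 0.205 | 0.92 | 0.223 | 1.004 |
| 20% spread | 0.225 | 0.201 | 0.89 | 0.224 | 0.996 |
| 20% early | 0.222 | 0.183 | 0.82 | 0.221 | 0.992 |
| 30% spread | 0.223 | 0.188 | 0.84 | 0.224 | 1.005 |
| 30% early | 0.220 | 0.166 | 0.75 | 0.216 | 0.985 |

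**Mechanism.** Among dropouts alone, the between-arm difference in 24-week change is about 1.7 to 1.8 points with complete data. Under the model as written it falls to about 0.7 to 0.8 (spread) or 0.2 to 0.3 (early). For 20% early dropout, 0.8 × 1.775 + 0.2 × 0.22 = 1.46, against a simulated 1.459. The ratio 1.459/1.775 = 0.82 matches the CAFS ratio in the table.

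**No true effect.** Both models give a win difference within about 0.007 of zero.

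**Other runs.** Further simulations with four- or eight-weekly visits gave 0.94 to 0.72 without treatment and 0.98 to 1.02 with it. An eight-weekly run at 15% to 35% dropout gave 0.91 to 0.74 and 0.97 to 1.04.

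**Against the CAFS at the last shared visit.** This was simulated with the same slope and SDs, 30% slowing and no deaths. Values are shares of the complete-data win difference. The recovered share is (imputed − shared visit)/(1 − shared visit).

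| Visits and dropout | Last shared visit | Imputed as written | Recovered |
|---|---|---|---|
| 4-weekly, spread, 15% | 0.88 | 0.91 | 0.03/0.12 = 25% |
| 4-weekly, spread, 25% | 0.80 | 0.86 | 0.06/0.20 = 30% |
| 4-weekly, spread, 35% | 0.75 | 0.80 | 0.05/0.25 = 20% |
| 4-weekly, early, 15% | 0.77 | 0.86 | 0.09/0.23 = 39% |
| 4-weekly, early, 25% | 0.64 | 0.76 | 0.12/0.36 = 33% |
| 4-weekly, early, 35% | 0.51 | 0.67 | 0.16/0.49 = 33% |
| 8-weekly, spread, 15% | 0.85 | 0.90 | 0.05/0.15 = 33% |
| 8-weekly, spread, 25% | 0.76 | 0.83 | 0.07/0.24 = 29% |
| 8-weekly, spread, 35% | 0.69 | 0.77 | 0.08/0.31 = 26% |

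Where every dropout has at least one post-baseline visit, the two analyses agree within 0.03, so little is recovered.

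**The case against.** A reader might infer that the imputed CAFS will come out weaker than the non-imputed CAFS, and so produce a false sign of sensitivity to dropout. The documents do not support that. Section 6.5.5 compares each non-imputed pair at the latest visit both members have, and that comparison is itself attenuated by dropout, as much or more. In the second table the imputed result is the larger one in every row.

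It can also be said that no decision depends on this analysis. That stands. Success rests on the Bayesian model, secondary testing on the mixed model and the log-rank test, and primary CAFS inference on the non-imputed version. The error is conservative: it vanishes under the null and does not raise the false-positive rate.

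Pooling might be deliberate, or the Master SAP might call for imputation by arm. Neither can be ruled out, because the Master SAP and the simulation report were not available. But Section 1 of the SAP makes this document authoritative over the Master SAP on such matters, and a programmer following it would code the explicit list. A conservative placebo-based analysis already exists in Section 6.5.8, and Section 6.5.5 gives this set a different purpose. Section 6.5.8 is a contrast, not a second instance of the fault.

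**Conclusion.** The omission is on the page, and its direction does not depend on the particular values assumed: when treatment has an effect, the imputed CAFS understates what a full 24-week comparison would show. The loss is about 6% to 28% of the win difference at 10% to 35% dropout. The harshest setting tried, 35% dropout all early with no deaths, gave a third (1 − 0.67). With treatment in the model the result is within a few percent of complete data. These sizes depend on assumed slopes, variances, 120 placebo participants and dropout unrelated to outcome. They were computed for an ALSFRS-R-like score; the same model is specified for SVC and both HHD measures, but no size was computed on those scales.

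This is a fault in a supplementary analysis, worth correcting because the repair is small. It is no ground for doubting the primary result, the hierarchical tests or the primary CAFS inference.

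**What to change.** In Section 6.5.5, add randomised treatment group to the covariates of the imputation regression, or state that imputation is carried out separately in each arm. Keep the reference-based assumption to Section 6.5.8. If pooling is intended, say so in one sentence and label the imputed CAFS as conservative. The cost is one phrase in the SAP and one term in the imputation code, with no new data and no change to any decision rule.

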#### **6.5.6** HHD0 and HHD0^2

Analyses of HHD0 are the same as specified in the M-SAP with the addition of parallel analyses of HHD0^2, with a separate analysis that includes baseline serum NfL level as an additional covariate, and with the clarification that time to zero strength for both analyses is interval censored between HHD assessments.

Inference from these analyses is supportive of inference from the repeated-measures linear mixed model for HHD upper and lower extremity scores.

#### **6.5.7** Quantitative Voice Measures

Given the high frequency of voice recordings, a repeated-measures analysis with unstructured covariance is overly flexible but the assumption of linear change required by the random-slopes

model may be overly rigid. To complement estimates from the random-slopes linear mixed model, quantitative voice characteristics will be analyzed in a linear mixed model in which the temporal profile for both fixed and random terms is modeled using cubic B-splines with knots at 8 and 16 weeks. The model will include fixed terms for B-splines (4 terms), treatment group (2 levels), treatment group × B-spline interaction, centered time since symptom onset and centered time since symptom onset × B-spline interaction, centered delta-FRS and centered delta-FRS × B-spline interaction, centered baseline riluzole use and centered baseline riluzole × B-spline interaction, and centered baseline edaravone use and centered baseline edaravone × B-spline interaction The model will include random regimen-specific intercepts and slopes with unstructured covariance, random participant-specific B-splines (5 terms) with unstructured covariance, and a first-order autoregressive structure for residuals. A simplified covariance structure assuming no regimen-level covariance, heterogeneous compound symmetric covariance among the random B-splines, conditional independence of residuals, or a combination of the three simplifying assumptions will be used if the full model fails to converge. The primary estimand will be the treatment-dependent difference in 24-week change from baseline. The estimate and its 95% Wald confidence bounds will be obtained by a linear contrast of adjusted means. A separate analysis will include centered baseline serum NfL level and the interaction of centered baseline serum NfL level and B-splines as additional covariates.

# 6.5.8 Placebo Multiple Imputation

Placebo multiple imputation analyses are the same as specified in the M-SAP and will be applied to ALSFRS-R total score, HHD upper and lower extremity percentages, and SVC.

The following SAS code specifies the imputation for an endpoint measured every 8 weeks:

where Wk00, Wk08, Wk16, and Wk24 are the values of a given efficacy endpoint at the Baseline, Week 8, Week 16, and Week 24 Visits, respectively, trtnd has a value of zero (0) for participants randomized to placebo, and x and y take appropriate values to specify the range of a given outcome measure (i.e., 0 and 48 for ALSFRS-R total score; 0 and . for HHD upper and lower extremity percentages and SVC).

Inference from these analyses is supportive of inference from the Bayesian shared-parameter, repeated-measures model for the primary endpoint and assess sensitivity to the missing data assumption of the repeated-measures linear mixed model for secondary endpoints in the FAS analysis set. A separate analysis will include centered baseline serum NfL level as an additional covariate in both imputation stages.

